8. STATISTICAL METHODS AND ANALYSIS

8.1. Statistical Methods

8.1.1. Analysis of Continuous Data

Summary statistics (number of patients, mean, standard deviation, median, maximum value, and minimum value) will be calculated. Additionally, the first and third quartile points will be calculated as summary statistics for the efficacy endpoints.

8.1.2. Analysis of Categorical Data

The frequency of each category (eg, number of patients) and its proportion will be calculated.

8.1.3. Analysis of Binary Data

Frequency and its proportion will be calculated. A two-sided 95% confidence interval (exact method) will be calculated in calculating the confidence interval of proportion.

8.2. Statistical Analysis

8.2.1. Patient’s Profile

- **Patient disposition**

The number of enrolled patients, patients who completed the investigation, patients in the safety analysis set, and patients in the efficacy analysis set will be summarized in enrolled patients. Additionally, the number of patients for whom the report form was not collected,

patients excluded from the safety analysis set, and patients excluded from the efficacy analysis set and number of patients by reasons for exclusion will be summarized.

- **List of discontinuations/dropouts**

The number and proportion of patients who discontinued the investigation by the time point of completed height follow-up (less than 1 year, 1 year or longer and less than 2 years, 2 years or longer and less than 3 years, --- and N years or longer and less than N + 1 years) will be summarized for the safety analysis set, efficacy analysis set, and eligible criteria set. Then, the number and proportion of patients will be summarized by the reason for discontinuation.

- **List of patients excluded**

The list of patients excluded from the safety analysis set, efficacy analysis set, and eligible criteria set will be prepared with the reason for exclusion.

8.2.2. Patient Characteristics and Treatment History

- **Patient characteristics**

The following patient characteristics will be summarized according to 8.1 for the safety analysis set, efficacy analysis set, and eligible criteria set.

- Gender [male, female].
- Age (continuous variable) [less than 5 years, 5 years or older and less than 7 years, and 7 years or older].
- Height of father (continuous variable).
- Height of mother (continuous variable).
- Mother's birth history [the first childbirth/multipara].
- Presence/absence of GHD family history.
- Twin/multiplets.
- Childbirth procedures [normal, breech presentation, Caesarean section, multiple selection].
- Fetus week number [less than 33 weeks, 33 weeks or older and less than 37 weeks, 37 weeks or older].
- Apgar score (1 minute) (continuous variable).
- Apgar score (5 minutes) (continuous variable).

- Apgar score (10 minutes) (continuous variable).
- Birth height (continuous variable).
- Birth weight (continuous variable) [less than 1000 g, 1000 g or higher and less than 2500 g, and 2500 g or higher].
- Birth head circumference (continuous variable).
- IGF-I (continuous variable).
- IGF-I SDS (continuous variable).
- Height (continuous variable).
- Height SDS (continuous variable) [less than -2.5 SD, -2.5 SD or higher].
- Height velocity (continuous variable): $365.25 \times (\text{height at start of treatment} - \text{Height at 1 year before start of treatment}) / (\text{Height measurement date at start of treatment} - \text{Height measurement date at 1 year before start of treatment})$.
- Height velocity SDS (continuous variable) [less than 0 SD, 0 SD or higher].
- Body weight (continuous variable).
- Body weight SDS (continuous variable).
- BMI (continuous variable).
- BMI SDS (continuous variable).
- Head circumference (continuous variable).
- Bone age (male) [less than 17 years, 17 years or older].
- Bone age (female) [less than 15 years, 15 years or older].

The following number and proportion of patients will be summarized by system organ class (SOC) and preferred term (PT) in the safety analysis set.

- Details of past histories.
- Details of concurrent disease.

The following number and proportion of patients will be summarized in the safety analysis set, efficacy analysis set, and eligible criteria set.

- Details of concomitant medications.

- Details of non-drug concomitant therapies.
- Details of pretreatment drugs.
- **Treatment status of Genotropin**

The following treatment status of Genotropin will be summarized in the safety analysis set.

- Dose at start (continuous variable) [less than 0.23 mg/kg/week, 0.23 mg/kg/week or higher and less than 0.35 mg/kg/week, 0.35 mg/kg/week or higher and less than 0.47 mg/kg/week, 0.47 mg/kg/week or higher]: Dose per week/kg body weight described at the starting date of the first treatment.
- Duration of treatment (continuous variable) [less than 1 year, 1 year or longer and less than 2 years, 2 years or longer and less than 3 years,---, N years or longer and less than N + 1 year]: (ending date of the last treatment - starting date of the first treatment + 1) /365.25.

The Duration of treatment is defined as the period from the first treatment day to the day of the last treatment confirmed in this investigation, including washout period.

To confirm the dose modification, the dose per week/kg, change in the dose from the start of Genotropin, and change in the dose from the previous year will be summarized at the start of Genotropin and once a year thereafter. The body weight value measured on the earliest date in each period will be used to calculate the dose per week/kg. The dose per week/kg will be considered as missing when there is no body weight measurement during the period.

8.2.3. Safety Analysis

8.2.3.1. Adverse Drug Reactions

- **All adverse drug reactions**

The number and proportion of patients who developed an adverse drug reaction will be summarized by SOC and PT.

- **Serious adverse drug reactions**

The number and proportion of patients who developed a serious adverse drug reaction will be summarized by SOC and PT.

- **Details on adverse drug reaction**

The number and proportion of patients who developed an adverse drug reaction will be summarized by SOC and PT for each of the following items.

- Seriousness [serious, non-serious].
- Known/unknown [known, unknown].

- Measures taken [permanently discontinued, temporarily discontinued, dose reduced, dose increased, no dose change].
- Outcome [not recovered, recovered with sequelae, resolving, disappeared/resolved, unknown].

When the same patient experiences the same adverse drug reaction (with the same PT) more than once, the adverse drug reaction will be handled as follows in summarizing the number of patients with the adverse drug reaction.

- Seriousness: The adverse drug reaction will be handled as serious when it develops as both serious and non-serious events.
 - Known/unknown: The adverse drug reaction will be handled as unknown when it develops as both known and unknown events.
 - Number of days before onset: The number of days before the adverse drug reaction developed for the first time.
 - Measures taken: When more than one measure has been taken, one of them will be employed with the order of preference of permanently discontinued, temporarily discontinued, dose reduced, and others (no measure/dose increased).
 - Outcome: The outcome of the event that developed last will be used.
- **Timing for development of adverse drug reaction**

The number of patients who develop an adverse drug reaction for the first time in less than 1 year after the start of treatment will be summarized by SOC and PT for patients who receive Genotropin for less than 1 year. Similarly, the number of patients who develop an adverse drug reaction for the first time during the period of 1 year or longer and less than 2 years after the start of treatment will be summarized by SOC and PT for patients who receive Genotropin for 1 year or longer and less than 2 years. The same will be repeated to summarize it for the period of 2 years or longer and less than 3 years and so on (N years or longer and less than N + 1 years).

The number of patients will be summarized cumulatively. For example, patients for whom the duration of treatment is 2 years or longer and less than 3 years will be included in patients for whom the duration of treatment is less than 1 year and those for whom the duration of treatment is 1 year or longer and less than 2 years.

- **Development status of adverse drug reaction by inclusion in safety analysis set**

A list of adverse drug reactions in patients excluded from the safety analysis set will be prepared for the patients for whom the report form is collected. Furthermore, the number of patients who develop an adverse drug reaction will be summarized by SOC and PT.

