- 3) Patients whose poor physical growth after birth is attributable to disease other than intrauterine growth retardation cannot be enrolled in this investigation. Also patients who are currently receiving treatment that is known to cause poor physical growth cannot take part in this investigation.

3. Target sample size

The target number of subjects from which data will be collected is 400.

Ver.2

4. Duration of investigation

The duration will be from April 2013 to March 2016 (3 years); provided that it may be extended depending on the progress of the investigation.

The investigation will be continued as long as the subject is receiving Genotropin, or as determined appropriate by the investigator.

5. Investigation procedures

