8.2.3.2. Adverse Event

- **All adverse events**

The number and proportion of patients who develop an adverse event will be summarized by SOC and PT.

- **Adverse events by seriousness**

The number and proportion of patients who developed serious adverse events will be summarized by SOC and PT. The number and proportion of patients who develop a non-serious adverse event will be summarized in the same manner.

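### Apart from a count of first-onset ADRs by treatment year, safety is summarized only as crude patient proportions, although exposure is unequal by design

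*SAP*

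**What the plan says.** **Safety tables.** For all ADRs, SAP 8.2.3.1 says: "The number and proportion of patients who developed an adverse drug reaction will be summarized by SOC and PT". Serious ADRs and the breakdowns by seriousness, expectedness, measures taken and outcome use the same measure. For AEs, SAP 8.2.3.2 says: "The number and proportion of patients who develop an adverse event will be summarized by SOC and PT", and repeats this for serious and non-serious events.

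**Methods.** SAP 8.1 provides summary statistics, frequencies and proportions. For binary data, "A two-sided 95% confidence interval (exact method) will be calculated in calculating the confidence interval of proportion". No incidence rate or time-to-event method is listed.

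**Exposure.** SAP 8.2.2 summarizes treatment duration in the safety analysis set, in bands that continue to N years: "Duration of treatment (continuous variable) [less than 1 year, 1 year or longer and less than 2 years". The definition reads "The Duration of treatment is defined as the period from the first treatment day to the day of the last treatment confirmed in this investigation," and ends "including washout period". On the calendar side, Protocol section 4 says: "The duration will be from April 2013 to March 2016 (3 years); provided that it may be extended depending on the progress of the investigation". It adds that the investigation continues for as long as the child is treated, or as the investigator sees fit. A new patient's assessment period goes back to the start of therapy, even when that precedes enrolment (Protocol 5.4.1). Transferred patients bring their data from the previous investigation into the analysis set (SAP 2.1).

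**The one exposure-related safety table.** The timing item in SAP 8.2.3.1 counts patients with a first-onset ADR in each treatment year, by SOC and PT, within duration groups. "The number of patients will be summarized cumulatively", so longer-treated children also belong to the earlier groups. In effect, the base for year k is everyone treated into year k. There is no counterpart for AEs or serious AEs.

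**The concern.** Long-term safety is half of the stated objective (Protocol section 1, SAP 2.2), and the results are meant for journals, conferences and the regulator. A child observed for six months and one observed for eight years each add one to the denominator, but the second has far longer in which to have an event. At an unchanged hazard, a cohort followed longer shows a higher proportion.

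This matters in three places. SAP section 3 plans an interim analysis to consider extending the investigation, so proportions can rise from interim to final simply because the same children have been followed longer. Published proportions will be set beside those of other growth hormone cohorts with different follow-up. And in the timing table, raw counts fall in later years because fewer children remain, which a reader could take for falling risk.

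**Working it through.** **Inputs.** The plan states no event rate, expected incidence or exposure distribution, and gives no derivation for its target of 400 (Protocol section 3; approximately 400 in SAP 2.1). There is no figure of the plan's to reproduce. From the documents: n = 400, and exposure bands from under 1 year upwards. Assumed: a constant hazard λ of 1, 2, 5 or 10 first events per 100 patient-years, and three exposure mixes.

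| Mix | Years of exposure (share of children) | Mean, years |
|---|---|---|
| Short | 0.5 (40%), 1.5 (30%), 3 (20%), 5 (10%) | 1.75 |
| Middle | 0.5 (15%), 1.5 (20%), 3 (35%), 6 (30%) | 3.2 |
| Long | 0.5 (5%), 3 (25%), 6 (40%), 9 (30%) | 5.9 |

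**Step 1: crude proportion.** With share w at exposure t, the proportion is Σ w·(1 − exp(−λt)).

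| λ per 100 patient-years | Short | Middle | Long | Long ÷ short |
|---|---|---|---|---|
| 1 | 1.7% | 3.2% | 5.7% | 3.3 |
| 2 | 3.4% | 6.2% | 11.0% | 3.2 |
| 5 | 8.2% | 14.5% | 24.8% | 3.0 |
| 10 | 15.2% | 26.1% | 42.6% | 2.8 |

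Ratios use unrounded proportions; for the first row, 5.675 / 1.725 = 3.29. At λ = 5 per 100 patient-years and n = 400, the exact 95% intervals are 5.7% to 11.4% (short, 33 children) and 20.6% to 29.3% (long, 99 children). They do not overlap, although the hazard is identical.

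Reading down a column, the middle mix goes from 3.2% to 26.1% as the hazard rises tenfold. The proportion therefore carries information on risk as well as follow-up.

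**Step 2: a two-point check at 2 per 100 patient-years.** 1 − exp(−0.02) = 0.01980 and 1 − exp(−0.12) = 0.11308.

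- 80% at 1 year, 20% at 6 years: 0.8 × 0.01980 + 0.2 × 0.11308 = 3.8%.
- 20% at 1 year, 80% at 6 years: 0.2 × 0.01980 + 0.8 × 0.11308 = 9.4%.

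**Step 3: person-time rate.** Expected person-years to first event are Σ w·(1 − exp(−λt))/λ per child. At λ = 0.05 this is 1.631 years (short) and 4.969 years (long). The rates are 0.08153 / 1.631 and 0.24844 / 4.969, both 5.0 per 100 patient-years. The dependence on the mix is gone.

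**Step 4: the timing table, if its counts were divided by the cumulative base.** Take exponential durations with mean T and let μ = 1/T. First events in year k divided by everyone treated into year k is λ/(λ+μ) × (1 − exp(−(λ+μ))) × exp(−λ(k−1)). At λ = 0.05:

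| T, years | Year 1 | Year 6 |
|---|---|---|
| 1.75 | 3.7% | 2.9% |
| 3.2 | 4.2% | 3.3% |
| 5.9 | 4.5% | 3.5% |

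Most of the dependence on the mix disappears. What remains reads below 5 per 100 patient-years, because children who leave during a year still count fully in its base. It also drifts down by exp(−0.25) = 0.78 from year 1 to year 6, because children with an earlier event stay in the base.

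**Step 5: the timing table as specified, counts only.** For T = 3.2 and n = 400, the expected first events are 400 × 4.2% = 16.8 in year 1. In year 6 about 85 children remain (400 × exp(−5/3.225)), giving 85 × 3.3% = 2.8. The count falls about sixfold at a constant hazard.

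**The case against.** A crude proportion is a legitimate description of how many children were affected over the observed period. The SAP is exploratory, with no significance level and no decision rule (sections 4.1 and 4.2), and it plans no safety comparison between entry routes or with another cohort. This stands, and it limits the severity.

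A reader might infer that the proportions show follow-up mix rather than risk. The documents do not support that: as Step 1 shows, the proportion also rises with the hazard within any fixed mix. It reflects both.

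A reader might also infer that the SAP ignores exposure. It does not. Treatment duration is summarized for the safety set with number and mean, so total treatment time, washout included, can be recovered as their product. The timing table has a definable base which, if printed, would remove most of the dependence on the mix for ADRs. But total treatment time is not time at risk to first event. The timing table specifies a number of patients only, and nothing comparable exists for AEs or serious AEs.

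Finally, SAP 8.2.3.4, within the safety analysis, is redacted. Whether it contains an exposure-adjusted analysis is unknown, so the point is confined to the visible text.

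**Conclusion.** The point holds in limited form. In the visible SAP, the ADR, AE and serious-event tables give crude proportions with no time denominator, while exposure is unequal by design. The only offset is an ADR timing table that gives counts and keeps children with an earlier event, or with only part of the year, in its base. The proportions are valid as descriptions but not as rates, nor for the comparisons a long-term safety report invites.

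The actual distortion is unknown. The 2.8- to 3.3-fold range rests on constant hazards and assumed exposure mixes. How long transferred patients had already been treated is not quantified in either document. This should be corrected before the final analysis, but it does not invalidate the planned tables.

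**What to change.** Keep the crude tables and amend SAP 8.1 and 8.2.3 as follows.

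1. Add first-event incidence rates per 100 patient-years with 95% confidence intervals for all ADRs, serious ADRs, all AEs and serious AEs, overall and by SOC. Give PT-level rates for the whole period only. Per-year PT rates in about 400 children would be mostly sparse cells.
2. Stop person-time at the first event, the end of treatment or the last AE report, whichever comes first. Ending at treatment stop fits Protocol 6.8, under which AEs during height follow-up are investigated only as the sponsor finds necessary.
3. In the timing table, print for each treatment year the number at risk (children without an earlier event) and the person-years. Extend the table to AEs and serious AEs.
4. State one rule for washout and interruptions, applied equally to events and person-time. Removing off-drug gaps from the denominator while still counting events that start in them would mismatch the two.

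Treatment periods (Protocol 6.3) and AE onset dates (Protocol 6.7) are already collected, so this investigation needs no new data items. The documents do not show how much interruption detail the previous investigation recorded for transferred patients, and the rule should allow for that. The cost is SAP wording, additional tables and programming, since each SOC and PT needs its own risk set. Intervals for rare events will be wide.

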6.6 Patient's profile

Eligibility for further treatment with Genotropin will be evaluated at the completion of assessment period for each booklet. If further treatment with Genotropin is not indicated, a major reason for treatment discontinuation should be selected from among the following options. If "Adverse event", "Laboratory abnormal", or "Death" is selected, relevant data should also be recorded in the adverse event section.

- [1] Reaching adult height (final height)
- [2] Reaching the standard height
- [3] Epiphyseal closure
- [4] Growth rate
- [5] Preference of patient/parent(s)
- [6] Non-compliance
- [7] Discontinuance of public funding

Ver.2

- [8] Change in diagnosis
- [9] Poor clinical response
- [10] Adverse event
- [11] Laboratory abnormal
- [12] Death
- [13] Lost to follow-up (specify "Names of center/department" if the reason for lost to follow-up is transfer to other hospital/department)
- [14] Others (the reason should be specified if "Others" is selected)

Treatment strategy as well as presence of other medication which has been switched to after discontinuation of Genotropin therapy should also be described for subjects completing or discontinuing Genotropin therapy.

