6.7. Adverse events

Pertinent to safety assessment, the status of adverse events after the commencement of Genotropin therapy should be verified and the following information should be recorded. Adverse events should be verified in principle until the assessment period for each booklet is completed. Upon occurrence of any adverse event, the investigator shall provide appropriate intervention, promptly report to Sponsor in accordance with "Adverse event reporting" (Attachment 1), and follow up on the progress and outcome in principle until the symptoms disappear. Also, the investigator shall quickly notify Sponsor, "if a patient or the patient's partner conceives, or it has been found out that a patient or the patient's partner has conceived, whether adverse event has occurred or not," "if a serious adverse event occurred," and if any follow-up information thereto related has been obtained. Refer to "Adverse event reporting" (Attachment 1) for the details of procedures.

Furthermore, any occurrence of intrauterine exposure, or a serious adverse drug reaction or an adverse reaction not described in the package insert should be separately investigated as determined necessary by Sponsor.

- [1] Presence/absence of adverse event
- [2] Name of adverse event
- [3] Date of onset
- [4] Intervention
- [5] Seriousness
- [6] Outcome
- [7] Causal relation with Genotropin

[The following variables should be recorded if the adverse event is associated with abnormal test results, e.g., clinical laboratory]

- [8] Laboratory parameter

Ver.2

[9] Site reference

[10] Unit

[11] Date of measurement

[12] Result

Note: An adverse event is any untoward medical occurrence in a subject following Genotropin dose (including clinically significant change in laboratory test results); the event needs not necessarily to have a causal relationship with the treatment. A serious adverse event is any untoward medical occurrence that; Results in death; Is life-threatening (immediate risk of death), Requires inpatient hospitalization or prolongation of existing hospitalization; Results in persistent or significant disability/incapacity; Results in congenital anomaly/birth defect; or otherwise may result in medically important event or disorder.

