7. HANDLING OF MISSING VALUES

Any missing data on the seriousness, measures taken, and outcome of adverse events will be handled as “unknown” in summarizing data.

Measured values outside the acceptable range (Appendix 1) at each evaluation time point of the efficacy endpoints and clinical laboratory parameters will be handled as missing and missing data will not be imputed.

The procedure to handle uncleaned data is described below.

- Items with missing data: Missing data will be handled as missing (“unknown” for the category of classification variables) for both tabulation and listing.
- Items with inconsistent data: Inconsistent data will be handled as missing for both tabulation and listing. In this regard, however, a data handling list will be prepared separately.
- No signature: Descriptions in the report form without signature of the contract physician (or with signatures of other physicians than the contract physician) will be handled as missing for both tabulation and listing. No date or inconsistent date in the signature date section (eg, date of signature before or after the start date of treatment) will be considered to indicate that there is no signature on the report form.

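### The outcome breakdown of adverse drug reactions has no fatal category, and the repeat-event rule gives a fatal outcome no priority

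*SAP*

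**What the plan says.** SAP 8.2.3.1, under the details on adverse drug reactions, sets the form of the table: "The number and proportion of patients who developed an adverse drug reaction will be summarized by SOC and PT for each of the following items". One of those items is "Outcome [not recovered, recovered with sequelae, resolving, disappeared/resolved, unknown", a bracketed list of five levels. SAP 8.1.2 gives the general method for categorical data: "The frequency of each category (eg, number of patients) and its proportion will be calculated".

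For a patient who has the same PT more than once, 8.2.3.1 gives one rule per item. The outcome rule is "Outcome: The outcome of the event that developed last will be used".

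SAP section 7 gives *unknown* its meaning: "Any missing data on the seriousness, measures taken, and outcome of adverse events will be handled as" unknown when data are summarised.

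The protocol provides for death in two places. In 6.7 it is the first criterion of seriousness: "A serious adverse event is any untoward medical occurrence that; Results in death; Is life-threatening (immediate risk of death". In 6.6 it is one of the listed reasons for stopping Genotropin, and when it is chosen, "relevant data should also be recorded in the adverse event section". Outcome is among the variables recorded there (6.7, item 6).

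**The concern.** Whether a reaction was fatal is basic information in a safety report. The investigation has long-term safety as a stated aim, and its data go to the regulator. The protocol requires a death to be entered with the adverse event data, but the table that classifies reactions by outcome has no place for it. A programmer following the SAP would have to put a fatal reaction beside non-fatal reactions that are still present, or beside reactions whose outcome was never reported. Either choice hides the most severe outcome and slightly distorts the level that receives it. The SAP does not say which to choose, so two programmers could produce different tables from the same data.

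**Working it through.** No sample size, error rate or event count enters this point, and the plan gives no figure to reproduce. The check sets the sections side by side.

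1. **Count the levels.** The outcome list has 5 levels, of which 0 are fatal and 0 are a residual such as *other*.

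2. **Is the list meant to be complete?** The SAP does not say so. But the bracketed lists in 8.2.2 (sex, age bands, birth-weight bands) are full sets of levels, and where a series is open the SAP shows it by running on to N years (duration of treatment, 8.2.2). The outcome list has no such mark. Reading it as complete is an inference, but the natural one.

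3. **Where could a fatal reaction go?** Three levels contradict a death: *recovered with sequelae*, *resolving* and *disappeared/resolved*. That leaves 5 − 3 = 2: *not recovered* and *unknown*. Section 7 uses *unknown* for missing outcomes, so putting a known death there would be a misuse. No rule in the SAP makes the choice.

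4. **Does the repeat rule protect a fatal outcome?** Under 8.2.3.1, serious prevails over non-serious, unknown (unlisted) over known, and the measures follow an order that starts with permanent discontinuation. Outcome alone follows time of onset. Suppose a patient has reaction A, then reaction B with the same PT while A is still present. A proves fatal and B is recorded with another outcome. B developed last, so B's outcome is tabulated. This sequence is narrow, but it means that a new level alone would not be enough.

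5. **Do other visible outputs show a fatal reaction?**

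| Output | What it would show |
|---|---|
| Serious adverse drug reactions (SAP 8.2.3.1) | The case, by SOC and PT, with no split by outcome |
| Adverse events by seriousness (SAP 8.2.3.2) | The case among serious events, with no split by outcome |
| Discontinuations by reason (SAP 8.2.1) | Possibly a count of deaths, not linked to PT or causality |
| Lists of serious reactions and serious events (SAP 9) | The patient; columns are not specified, so outcome may or may not appear |
| SAP 8.2.3.4 | Redacted; cannot be checked |

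The case stays in the report, but no visible summary table says which PT was fatal.

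**The case against.** The strongest reply is that a fatal reaction would not be lost. It is serious by the protocol's definition, so it enters the serious-reaction and serious-event tables and both patient lists. The death may also be counted among reasons for discontinuation, and the protocol requires serious events to be notified quickly to the sponsor. All of this stands. It limits the point to the outcome table, but does not supply the missing level.

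It can also be said that the investigation is descriptive (SAP 4.1), that death appears in the protocol only within a generic list of reasons and a standard definition, and that there may be no fatal reaction. This stands too: the protocol provides for deaths, but does not predict any.

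Three stronger readings are tempting, and the documents do not support them.

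- A reader might infer that the table would report zero fatal reactions among the target of 400 patients and attach a confidence limit to that zero. A table without a fatal row reports nothing about fatal reactions, and SAP 8.1.2 plans no interval for an item with several categories.
- A reader might infer that reactions with missing seriousness or missing measures drop out, because those two lists print no *unknown* level. Section 7 already supplies that level for summaries, other bracketed lists also leave it unprinted, and an event with missing seriousness still counts in the table of all adverse events.
- A reader might infer that deaths appear nowhere else in the planned output. The table of discontinuations by reason may count them.

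**Conclusion.** The point holds for the outcome table in SAP 8.2.3.1 and for its repeat-event rule. As written, a fatal reaction has no correct level, and a fatal outcome has no priority over that of a later-onset reaction with the same PT. Any fatal reaction would be affected. If none occurs the effect is nil, and the documents give no expected number, so the size cannot be stated further.

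The conclusion assumes that the bracketed list is complete and that the redacted section 8.2.3.4 does not tabulate fatal reactions. The text of the protocol's attachment on adverse event reporting is not available either. This is a small correction to a classification rule. It does not show that deaths would go unreported.

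**What to change.** In SAP 8.2.3.1, change the item to: Outcome [fatal, not recovered, recovered with sequelae, resolving, disappeared/resolved, unknown]. This makes 5 + 1 = 6 levels. In the rule for repeated reactions, add that a fatal outcome of any occurrence takes precedence within the same patient and PT, and that the last-event rule applies otherwise.

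The cost is two short edits to the SAP and one extra table row. Outcome is already recorded under protocol 6.7, and death as a reason for stopping under 6.6. Protocol 6.7 does not show the response options for outcome, so the sponsor should confirm that the report form can mark a particular reaction as fatal.
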